#### **10.2.2 Definition of Adverse Reaction**

An AR is defined as any MAE caused by the use of a pharmaceutical product. ARs are a subset of all suspected MAEs for which there is reason to conclude that the pharmaceutical product caused the event.

#### **10.2.3 Definition of Suspected Adverse Reaction**

Suspected adverse reaction (SAR) means any MAE for which there is a reasonable possibility that the study treatment caused the MAE. *Reasonable possibility* means there is evidence to suggest a causal relationship between the study treatment and MAE. An SAR implies a lesser degree of certainty about causality than AR, which means an MAE caused by a study treatment.

#### **10.2.4 Definition of Unexpected Medically-Attended Adverse Event or Unexpected Suspected Adverse Reactions**

An MAE or SAR is considered *unexpected* if it is not listed in the Investigator's Brochure or USPI or is not listed at the specificity or severity that has been previously observed.

## 10.3 Serious Adverse Events

### 10.3.1 Definition of Serious Adverse Events

An MAE is considered an SAE if it meets any of the following criteria:

- Results in death;
- Is life-threatening;

Note: An MAE or SAR is considered *life-threatening* if, in the view of either the investigator or sponsor, its occurrence places the subject at immediate risk of death. It does not include an MAE or SAR that, had it occurred in a more severe form, might have caused death;

- Requires in-patient hospitalization or prolongs existing hospitalization;
- Results in persistent or significant disability or incapacity;

That is, the event severely or permanently disrupts the subject's ability to perform normal life functions or daily activities.

- Results in a congenital anomaly or birth defect;
- Is medically significant (Important Medical Event);

Medical and scientific judgment should be exercised in deciding whether SAE reporting is appropriate in other situations, such as important medical events that may not be immediately life-threatening or result in death or hospitalization but may jeopardize the subject. Examples of such events are allergic bronchospasm requiring treatment in an emergency room, serious blood dyscrasias, or seizures/convulsions that do not result in hospitalization. The development of drug dependence or drug abuse would also be examples of important medical events.

### 10.3.2 Serious Adverse Event Reporting Requirements

Any SAE that occurs from the time the consent is signed through EOS Visit, whether or not the SAE is related to the study treatment, **must be reported to Dynavax or its designee within 24 hours of investigator awareness of the event**. The contact information for reporting SAEs is provided in the Study Reference Manual. General SAE reporting instructions are as follows:

- Submit SAE documents according to instructions in the Study Reference Manual.
- Record all SAEs on the MAE eCRF.
- For SAEs, record the primary event on the MAE eCRF; describe events occurring secondary to that primary event on the SAE form in the narrative description of the case.
- Death is an outcome, not an event. Record the event that resulted in the death as the fatal event on the MAE eCRF.
- For hospitalizations for surgical or diagnostic procedures, record the illness leading to the surgical or diagnostic procedure as the SAE, not the procedure itself. Capture the procedure in the narrative as part of the action taken in response to the illness.
- Elective hospitalizations will not be considered SAEs and do not need to be reported. Complications that prolong elective hospitalizations should be recorded as SAEs. Emergency room visits of less than 24 hours do not meet the criterion of hospitalization for SAE reporting purposes.

The SAE report should contain, at a minimum, the following information:

- Subject identifiers (ie, subject number)
- Suspected medicinal product
- MAE term (must be listed as serious)
- Contact information for person reporting event

The relationship of the SAE to study treatment will be assessed by the investigator (Section 10.4.2). Follow-up information should be actively sought and submitted as it becomes available.

The investigator will assess relationship to study treatment. In addition, the sponsor will assess relationship to study treatment and determine expectedness to HEPLISAV-B based on the current HEPLISAV-B Investigator's Brochure and USPI. The sponsor will report all HEPLISAV-B suspected unexpected serious adverse reactions (SUSARs) to regulatory authorities as expedited reports in accordance with applicable regulatory requirements

(eg, 21 CFR 312.32[c] and 314.80[e] in the US). All other SAEs will be reported as part of regulatory safety updates, as required, such as in annual reports.

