## **10.2 Adverse Events**

An AE is any untoward medical occurrence associated with the use of a drug, whether or not considered drug-related. An AE can therefore be any unfavorable and unintended sign (including a clinically significant abnormal laboratory finding), symptom, or disease temporally associated with the use of a medicinal (investigational) product, whether or not related to the study treatment. In this trial, only MAEs, AEs for which a subject seeks medical attention at a doctor’s office, clinic, study site, emergency room, or is hospitalized, will be collected.

Medical conditions present at Screening (ie, before informed consent is obtained) or present before the first study treatment (Day 1) are not MAEs and are not recorded on the MAE eCRF. These medical conditions should be adequately documented on the Medical History eCRFs. Any increase in severity or frequency of a medical condition documented as medical history after the first study treatment will be recorded as an MAE and will be captured on the MAE eCRF.

An uncomplicated pregnancy is not an MAE or SAE and should not be reported as an MAE/SAE. Subjects should be followed as described in Section [10.5](#).

The reporting period for all non-serious MAEs begins at the time of the first study treatment (Day 1) through EOS Visit. All MAEs will be captured on the MAE eCRF.

MAEs should be documented in terms of a single medical diagnosis. When this is not possible, the MAE should be documented in terms of signs and/or symptoms observed by the investigator or reported by the subject at each study visit.

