4.0 ANALYSIS VARIABLES

Primary Endpoints

- Proportion of subjects with treatment-emergent MAEs
- Proportion of subjects with treatment-emergent SAEs, acute myocardial infarctions (AMIs), or deaths
- Proportion of subjects with treatment-emergent immune-mediated adverse events of special interest (AESIs)
- SPR at Week 20

Secondary Endpoints

- Proportion of subjects with anti-HBs concentration ≥ 100 mIU/mL
- Anti-HBs geometric mean concentration (GMC)
- SPR at each study visit through 20 weeks after the first dose of study vaccine

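### The elective-admission exception in protocol 10.3.2 is not limited to unchanged baseline conditions, so some new or worsened illness can drop out of the primary SAE proportion

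*Protocol*

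**What the plan says.** Four parts of the protocol bear on a planned hospital admission.

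- **10.2** makes an event an MAE if the subject seeks medical attention or is hospitalized. Conditions "present before the first study treatment (Day 1) are not MAEs and are not recorded on the MAE eCRF", but a later rise in the severity or frequency of such a condition is an MAE.
- **10.3.1** opens with "An MAE is considered an SAE if it meets any of the following criteria", and one criterion is "Requires in-patient hospitalization or prolongs existing hospitalization". It does not separate scheduled from unscheduled admissions.
- **10.3.2, procedure bullet:** when the admission is for surgery or a diagnostic procedure, sites are to "record the illness leading to the surgical or diagnostic procedure as the SAE, not the procedure itself". Again there is no distinction by scheduling.
- **10.3.2, next bullet:** "Elective hospitalizations will not be considered SAEs and do not need to be reported". It continues: "Complications that prolong elective hospitalizations should be recorded as SAEs". The same bullet says that emergency room visits shorter than 24 hours do not count as hospitalization.

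The endpoint that depends on these rules is primary in protocol 4.2.1 and SAP 4.0: "Proportion of subjects with treatment-emergent SAEs, acute myocardial infarctions (AMIs), or deaths". SAP 7.1 restates the SAE collection period, and SAP 9.7 lists the SAE tables. Neither defines an elective admission or says which bullet prevails.

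**The concern.** An exception for elective admissions normally serves to keep planned care for stable, pre-existing disease from being counted as a safety event. This one is worded more widely. It turns on how the admission was arranged and not on whether the illness is new. A condition that first appears or worsens after vaccination and is treated on a booked date therefore falls inside it.

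The result feeds a primary safety endpoint in a single-arm study, where no comparator group carries the same classification error. The synopsis lists 25 centers, and each can settle the question for itself, so the pooled proportion may mix two definitions. An event left unreported as an SAE also misses notification to the sponsor within 24 hours and the sponsor's own assessment of causality and expectedness.

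**Working it through.** This is a question of wording. The plan states no figure for it, so there is none to reproduce. The first step is to run the possible kinds of admission through each rule.

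| Admission | MAE (10.2) | SAE by hospitalization (10.3.1) | Procedure bullet (10.3.2) | Elective bullet (10.3.2) | Do the rules agree? |
|---|---|---|---|---|---|
| Scheduled, baseline condition unchanged | No | No, because it is not an MAE | Not reached | Not an SAE | Yes |
| Unscheduled, new or worsened illness | Yes | Yes | Illness is the SAE, if admitted for a procedure | Does not apply | Yes |
| Scheduled, new or worsened illness that also meets another seriousness criterion | Yes | Yes | Illness is the SAE, if admitted for a procedure | Discounts the admission only | Yes: still an SAE by the other criterion |
| Scheduled, new or worsened illness that meets no other criterion | Yes | Yes | Illness is the SAE, if admitted for a procedure | Not an SAE, need not be reported | **No** |

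The conflict is confined to the last row.

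The second step is the effect on the endpoint. Inputs:

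- Denominator n = 115, the planned enrolment in protocol 11.1. This assumes that every enrolled subject enters the Safety Population.
- k = number of subjects whose only qualifying event is a last-row admission. A subject with another SAE, an AMI or a fatal outcome is already counted, so the classification changes nothing for that subject.

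Shift in the proportion = k/n. For one subject this is 1/115 = 0.0087, or 0.87 percentage points.

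The documents give neither an SAE rate nor a rate of planned admissions, so the table below is illustration only. It assumes that 35 of 115 subjects have an event without the disputed admissions, and it uses exact (Clopper-Pearson) 95% limits. The same routine at N = 100 reproduces all four rows of protocol Table 11-1 (for example 80%: lower limit 70.8%, width 0.165).

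| k (assumed) | Proportion | Exact 95% CI | Shift (points) |
|---|---|---|---|
| 0 | 30.4% | 22.2 to 39.7 | 0 |
| 1 | 31.3% | 23.0 to 40.6 | 0.9 |
| 3 | 33.0% | 24.6 to 42.4 | 2.6 |
| 6 | 35.7% | 26.9 to 45.1 | 5.2 |
| 12 | 40.9% | 31.8 to 50.4 | 10.4 |

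The shift is k/115 whatever starting count is assumed. Nothing in the documents says which row is realistic.

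**The case against.** The strongest reply is that the three texts can be read together: a general definition in 10.3.1, a rule on how to name the event in the procedure bullet, and a specific exception in the bullet after it. On that view only one term lacks a definition. This stands in part, and it is why the point is an undefined boundary between overlapping rules and not a flat contradiction. It does not remove the problem. It works only if the word non-elective is read into the procedure bullet, and it then makes seriousness depend on the booking and not on the illness. It also sits badly with Table 10-1 (SAP Table 9-1), which puts hospitalization at Grade 4 for events outside the CBER scale. The same admission could appear among the events of Grade 3 or above and be absent from the SAE table.

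A second reply is that little is lost. This stands as a limit on size. The exception leaves the other seriousness criteria in place, including important medical events. AMIs are a separate part of the composite and are reviewed by the Safety Monitoring Committee. Potential AESIs go to the sponsor within 72 hours whether serious or not. Complications that prolong an elective stay remain SAEs. The illness itself is still an MAE, so the primary MAE proportion should be unaffected if 10.2 is followed. All analyses are descriptive (SAP 9.0), so no test or decision rule changes.

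Third, the Study Reference Manual governs SAE submission and is not among the documents reviewed. It may tell sites what elective means. That cannot be excluded, but the definition of a primary endpoint should not rest on it alone.

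A reader might also infer the opposite error: that the procedure bullet turns routine care of baseline kidney disease, such as access surgery, into SAEs. The documents do not support this. An SAE must first be an MAE (10.3.1), and a condition present before Day 1 is not an MAE unless it has worsened (10.2).

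**Conclusion.** The point holds for one class of event: a scheduled in-patient admission for an illness that began or worsened on study and meets no other seriousness criterion. 10.3.1 counts it, the elective bullet excludes it, and no text says which prevails. Following the elective bullet as written under-counts a primary endpoint and bypasses 24-hour reporting for those events.

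The size is 0.87 points for each affected subject with no other SAE, AMI or death, assuming 115 subjects in the Safety Population. The total cannot be set from the documents.

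A reader might infer a bias of several points by supposing, say, that 5% to 15% of subjects have a planned admission and, independently, 30% to 50% have another SAE. The arithmetic then runs from (1 − 0.50) × 0.05 = 2.5 points to (1 − 0.30) × 0.15 = 10.5 points. Those rates appear nowhere in the documents. The calculation also treats every planned admission as disputed, when only those in the last row of the first table are, and positive correlation with other SAEs would shrink the result. It shows sensitivity and is not an estimate.

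This is a reporting-definition gap of moderate importance. It is worth correcting because the endpoint is primary and the correction is small.

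**What to change.** Change only the first sentence of the elective bullet in protocol 10.3.2, to:

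> *An elective hospitalization is exempt from SAE reporting only if it is for a condition that was present before informed consent and has not increased in severity or frequency since. An in-patient hospitalization, scheduled or not, for a condition that began or worsened after consent is an SAE and is recorded under that condition.*

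Keep the existing sentences on complications that prolong an elective stay and on emergency room visits under 24 hours. The cut-off is consent and not first injection because SAEs are collected from consent. A first-injection cut-off would exempt serious illness that arises during screening. Worsening overrides any earlier booking, so an admission planned before entry for a condition that later deteriorates is not exempt.

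Repeat the rule in SAP 7.1, and state there that treatment-emergent status is still counted from the first injection. SAEs arising between consent and Day 1 are then reported but do not enter the primary proportion.

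For data already collected, list all MAEs with a hospital admission and review them against this rule before final database lock.

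The cost is one amended protocol sentence, one SAP sentence and one review listing. Sites may file a few more SAE reports, and the reported SAE rate may rise. Events that sites never recorded cannot be recovered by the review.

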#### **10.4 Medically-Attended Adverse Event Severity and Relationship to Study Treatment**

##### **10.4.1 Severity Grading of Medically-Attended Adverse Events and Abnormal Laboratory Test Results**

The severity of MAEs and laboratory abnormalities will be graded based on the United States Food and Drug Administration's (FDA) Guidance for Industry: Center for Biologics Evaluation and Research (CBER) Toxicity Grading Scale for Healthy Adult and Adolescent Volunteers Enrolled in Preventive Vaccine Clinical Trials in [Appendix 3](#) (with the exception of malaise, which will be graded per CTCAE v4.03), with the modification that, by convention, all fatal MAEs will be graded as Grade 5 (Fatal).

All MAEs not listed in the CBER toxicity grading scale will be graded as shown in Table 10-1.

**Table 10-1: Grading Scale for Medically-Attended Adverse Events Not Included in the CBER Guidance on Toxicity Grading for Healthy Volunteers in Vaccine Clinical Trials**

MAE Severity	Definition
Grade 1 – Mild	No interference with activity
Grade 2 – Moderate	Some interference with activity, not requiring medical intervention
Grade 3 – Severe	Prevents daily activity and requires medical intervention
Grade 4 – Potentially life-threatening	Emergency room visit or hospitalization
Grade 5	Death

*For all MAEs and SAEs, if there is a change in the severity after onset, the event should be reported as a single entry with the maximum severity grading captured.*

##### **10.4.2 Relationship of Medically-Attended Adverse Events to Study Treatment**

The investigator will determine the relationship of the MAE to study treatment using the definitions provided in [Table 10-2](#).

**Table 10-2 Definitions for Relationship of Medically-Attended Adverse Events to Trial Treatment**

Relationship to Trial Treatment	Definition
Not Related	Another cause of the event is most plausible; or clinically plausible temporal sequence is inconsistent with the onset of the event and the trial treatment administration; or a causal relationship is considered biologically implausible.
Possibly Related	An event that follows a reasonable temporal sequence from administration of the trial treatment or a known or expected response pattern to the suspected drug, but that could readily have been produced by a number of other factors.
Probably Related	An event that follows a reasonable temporal sequence from administration of the trial treatment, and there is a biologically plausible mechanism for trial treatment causing or contributing to the MAE, and the event could not be reasonably explained by the known characteristics of the subject's clinical state. In addition, the relationship may be confirmed by improvement on stopping the trial treatment and reappearance of the event on repeated exposure.

MAE = medically-attended adverse event.

The investigator will follow all MAEs observed during the study until the MAEs are considered resolved, stabilized, or until the subject has completed the study. The sponsor may request additional follow-up on specific unresolved MAEs.

If the SAE is assessed as possibly or probably related to study treatment, it must be followed until it is considered stable or resolved, including beyond EOS Visit.

Any SAE assessed as not related to study treatment will be followed as clinically indicated until its resolution or, if nonresolving, until it is considered chronic or stable, or until study completion.

The sponsor may request additional follow-up on specific unresolved MAEs.

## 10.5 Reporting and Documentation of Pregnancy

Any subject who becomes pregnant or begins breastfeeding during the study will be discontinued from all study treatments and will be followed for pregnancy outcome. Follow-up information should be actively sought by the investigator and submitted to Dynavax or designee as soon as it becomes available. The investigator will complete the pregnancy reporting form and all other relevant eCRFs. Uncomplicated pregnancies are not considered an MAE/SAE. A complicated pregnancy or a pregnancy with an adverse outcome may meet criteria for an MAE or SAE and would then also be reported according to the appropriate requirements.

A subject who becomes pregnant will be instructed to report the pregnancy to the study site as soon as possible. The subject should be followed by the investigator through the pregnancy (including beyond EOS) for outcomes. A report of the pregnancy will be completed by the investigator or designee and will document details of the pregnancy, outcome of pregnancy, and details of delivery.

Pregnancies and breastfeeding that occur from Day 1 through the end of the study (Week 68) must be reported by the investigator. The sponsor or designee must be notified as soon as possible once the study site learns of a pregnancy or breastfeeding. Pregnancy report forms provided by the sponsor or designee must be completed and submitted to Dynavax or designee. The contact information for reporting pregnancy is provided in the Study Reference Manual.

## **11.0 STATISTICAL METHODS**

This section outlines the statistical analysis strategy and procedures for the study. If, after the study has begun, changes are made to primary or exploratory objectives and/or hypotheses, or to the statistical methods related to those objectives and/or hypotheses, then those changes, along with an explanation as to when and why they occurred, will be listed in the Clinical Study Report (CSR) for the study. Post-hoc exploratory analyses will be clearly identified in the CSR. Handling of missing data, if any, will be outlined in the study Statistical Analysis Plan. Additional details of the statistical analyses to be performed will be provided in the study Statistical Analysis Plan.

### **11.1 Sample Size Considerations**

The sample size calculation is based on approximately 100 subjects in the per-protocol population (Table 11-1). With an expected 15% loss to follow up prior to week 20, approximately 115 subjects will be enrolled. This sample size would allow estimating immunogenicity response at the following accuracy levels depending on the observed immunogenicity responses.

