**Table 11-1: Sample Size Estimates**

N	If Observed Immunogenicity Response is	Width of the Resulting 95% Confidence Interval	Lower Limit of the Resulting 95% Confidence Intervala
100	80.0%	0.165	70.8%
100	86.0%	0.145	77.6%
100	90.0%	0.127	82.4%
100	95.0%	0.096	88.7%

N = number of subjects

a Calculation based on exact method (Clopper-Pearson)

Note: Approximately 115 subjects will be enrolled to meet the N of 100 evaluable subjects in the per-protocol population.

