## **11.4 Immunogenicity Analyses**

Immunogenicity data will be analyzed based on the PP Population. The SPR at specified timepoints will be estimated. The associated 2-sided 95% confidence interval will be calculated using the Clopper-Pearson method.

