6.3 Efficacy Population

The per-protocol (PP) population for the immunogenicity analysis will comprise all subjects who receive all study injections, have no major protocol deviations (see Section 9.2), and have anti-HBs levels obtained within the study visit window at Week 20. PP population is defined for Week 20 visit, but will be used in analyses at other visits where applicable.

The modified intent-to-treat (mITT) population for the immunogenicity analysis will comprise all eligible subjects who receive at least 1 study injection and have at least 1 post-injection immunogenicity evaluation.

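### Enrolling about 115 with 15% loss to follow-up gives about 98 subjects, not 100, before other per-protocol exclusions: a minor error in the sample-size statement with negligible effect on precision

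*Protocol*

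**What the plan says.** The sample-size rationale appears in the statistical methods part of the protocol synopsis, in Protocol 11.1 with Table 11-1, and in SAP 5.0 with Table 5-1. All start from a target of roughly 100 subjects in the PP population. Protocol 11.1 then says: "With an expected 15% loss to follow up prior to week 20, approximately 115 subjects will be enrolled". The note under Table 11-1, repeated in the synopsis and the SAP, gives the purpose: "Approximately 115 subjects will be enrolled to meet the N of 100 evaluable subjects in the per-protocol population".

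The PP population under SAP 6.3 "will comprise all subjects who receive all study injections, have no major protocol deviations", and it also needs an anti-HBs result within the Week 20 window. SAP 9.2 counts as major deviations an unmet enrolment criterion, a Week 20 sample outside ±7 days, and specified prohibited medication from 28 days before the first injection through Week 20.

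For the primary immunogenicity endpoint, Protocol 11.4 says: "The associated 2-sided 95% confidence interval will be calculated using the Clopper-Pearson method". SAP 9.0 states that no hypothesis will be tested.

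**The concern.** Two things do not match. First, the enrolment figure, the loss rate and the target cannot all hold: applying the stated loss to the stated enrolment leaves fewer than 100.

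Second, the allowance is for loss to follow-up, but the target is a PP count. Some subjects leave the PP population while still being followed. Protocol 7.2 and 8.1 provide for subjects to stop injections, for example after prohibited treatment or certain adverse events, and remain in the study for safety follow-up. If that happens before the fourth injection, they are not PP, yet they are not lost.

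With no hypothesis test, the precision table is the whole quantitative case for the sample size. The step from subjects enrolled to subjects analysed should therefore follow from the plan's own inputs.

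**Working it through.** **Inputs.** Target PP N about 100, loss 15%, enrolment about 115 (Protocol 11.1; SAP 5.0). Two-sided 95% Clopper-Pearson interval (Protocol 11.4; SAP 9.6).

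**Step 1: reproduce the plan's figures.** The enrolment figure is matched by N x (1 + d) = 100 x 1.15 = 115. The documents do not show the derivation, but this reproduces it exactly. The Clopper-Pearson limits for x responders of n are the 2.5% quantile of Beta(x, n − x + 1) and the 97.5% quantile of Beta(x + 1, n − x). At n = 100 they reproduce all four rows of Table 11-1.

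**Step 2: check the enrolment figure.**
- Expected number retained: 115 x (1 − 0.15) = 97.75, about 98.
- Enrolment needed for 100 after 15% loss: 100/(1 − 0.15) = 117.6, so 118, three more than planned.
- Largest share that can be non-evaluable if 115 are to yield 100: (115 − 100)/115 = 15/115 = 13.0%, from all causes together. That is below the 15% expected from loss alone.

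**Step 3: effect on precision of N = 98.** Same observed rates as the plan's table. Responder counts at n = 98 are fractional, so these are interpolated values.

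| Observed rate | Width, N = 100 | Width, N = 98 | Lower limit, N = 100 | Lower limit, N = 98 |
|---|---|---|---|---|
| 80% | 0.165 | 0.167 | 70.8% | 70.7% |
| 86% | 0.145 | 0.147 | 77.6% | 77.5% |
| 90% | 0.127 | 0.129 | 82.4% | 82.3% |
| 95% | 0.096 | 0.098 | 88.7% | 88.6% |

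**Step 4: further PP exclusions (assumed rates).** The documents give none, so this only shows a range. If a further 5%, 10% or 15% of the retained subjects failed PP, N would be 97.75 x 0.95, 0.90 or 0.85, which is about 93, 88 or 83. At an 86% response the width would be 0.151, 0.155 or 0.160, and the lower limit 77.3%, 77.0% or 76.6%. If the same percentages applied to all enrolled subjects, N would be 115 x 0.80, 0.75 or 0.70 = 92, 86.25 or 80.5. At N = 80 and 86% the width is 0.163 and the lower limit 76.4%.

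**The case against.** The strongest reply is that nothing of substance changes. Both 100 and 115 are given as approximate; 98 is within about 2% of 100, and 118 is three subjects more than 115. The shift in Step 3 is smaller than the effect of one subject's result: at n = 98, 84 responders give a lower limit of 77.2% and 85 give 78.4%, either side of the tabulated 77.6%. The reported interval will use the achieved N, so the result is neither biased nor misreported. All of this stands, and it limits the point to a minor one.

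The further exclusions also overlap with the stated loss, since a subject lost before Week 20 has no Week 20 sample and may have missed injections. SAP version 2.1 narrowed PP exclusion as well: injections given outside the visit window at Weeks 4, 8 and 16 no longer count as major deviations for this purpose. So the omitted exclusions are not wholly additional to the 15%.

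A reader might infer three stronger things that the documents do not support:
- **That the precision table is wrong.** Each row is labelled N = 100 and is correct for that N. Only the link from 115 enrolled to 100 PP fails.
- **That the trial will probably miss its target in a way that matters.** With independent 15% loss, the chance that at least 100 of 115 remain is 33%. But this treats an approximate target as a hard floor: 118 enrolled would reach 100 only 59% of the time, and 115 enrolled gives at least 95 with probability 80%.
- **That precision is materially overstated.** Anything beyond the N = 98 figures rests on exclusion rates the plan does not give. Even N = 83 lowers the limit at 86% by only 1.0 point.

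What the reply does not remove is that the stated inputs do not yield the stated output, and that the allowance is worded for a narrower set of losses than the PP definition creates.

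**Conclusion.** Wrong as written, but minor. On the plan's own inputs, 115 enrolled yields about 98 subjects after loss to follow-up, and the further PP exclusions have no stated allowance. The arithmetic is certain and needs no outside assumption. The cost in precision at N = 98 is negligible: 0.001 to 0.002 in width and about 0.1 point in the lower limit. A larger cost is possible but cannot be sized from the documents. No test, margin or success criterion is affected, and there is no case here for enrolling more subjects.

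**What to change.** Make one of two changes, in the same words, in the synopsis, Protocol 11.1 and Table 11-1, and SAP 5.0 and Table 5-1.

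- **Restate the yield.** Say that about 115 enrolled with 15% loss to follow-up gives about 98 subjects before other PP exclusions, and base the precision table on N = 98 using the values in Step 3.
- **Keep N = 100.** Say that 115 enrolled allows at most 13% (15/115) non-evaluable for the PP population from all causes. The 15% loss assumption cannot then stand beside it unchanged, so that sentence must be revised too.

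The first needs no new assumption and is the simpler. Rows for smaller N, such as 93 or 88, are optional; if added, label them as resting on assumed exclusion rates and state whether the rate applies to retained or enrolled subjects. The cost is a sentence and a table in each document, with very slightly less favourable stated precision.
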